**Table 21-1 Definition of years after the first Ozurdex injection in the Study eye**

Year # [a]	Year definition [b]
Year 1	Days [2, 365]
Year 2	Days [366, 731]
Year 3	Days [732, 1096]

---

- [a] As per protocol all patients will have at least 1 complete year of follow-up at the site and the maximum number of complete years will be 3. The 1st Ozurdex injection should occur after 1 January 2015 and data will be collected up to 1 September 2018.
- [b] Relative to the date of the first Ozurdex injection in the study eye. Day 1 = the date of the first Ozurdex injection in the study eye. There is no Day 0.

#### Time window (in weeks) after each Ozurdex injection in the study eye

For each Ozurdex injection in the study eye, follow-up visits performed at 7-12 weeks (+/- 2 weeks) (Days [35, 98]) after injection will be described. The time window of 7-12 weeks is relative to the date of each Ozurdex injection in the study eye, where Day 1 = date of the injection (there is no Day 0).

For IOP, BCVA and CRT, which are collected at follow-up visits, the date of assessment is the date of the follow-up visit at which they are reported. Therefore, for each Ozurdex injection, these parameters will be described at the date of assessment and 7-12 weeks after injection. If there is more than one assessment within the 7-12 week time window, then the mean value will be used for analysis considering IOP in mmHg, BCVA in approximate ETDRS letters, and CRT in  $\mu\text{m}$ .

For HbA1c, the date of assessment is collected at follow-up visits. However, assessment of HbA1c will be presented only at baseline and last study visit.

### **21.3 DERIVED VARIABLES**

Derivation details of all variables that will be derived in analysis datasets are defined in this section. Derived variables are identified in square brackets ([DV]) in the other sections of the SAP.

### 21.3.1 Variables related to Anti-VEGF and Corticosteroids Treatments

#### Identification of anti-VEGF and Corticosteroids treatments

Prior and concomitant anti-VEGF and Corticosteroids treatments will be identified from treatments reported in the following sections of the eCRF: '*Prior intravitreal injections/Corticosteroids in Study eye*' (PII/F6 form), and '*Concomitant Medications (inclusive of intravitreal injections, systemic Steroids, and IOP medications)*' (CM/F18 form).

In these sections, anti-VEGF treatments will be identified as:

- pre-listed treatments: Avastin®, Lucentis®, Eylea® and Macugen®,
- treatments reported in the category 'Other anti-VEGF therapy'

and corticosteroids will be identified as:

- pre-listed treatments: Triamcinolone® and Iluvien®,
- treatments reported in the category 'Other corticosteroid therapy'.

#### Number of anti-VEGF treatments in the study eye prior to the first Ozurdex implant injection in the study eye

The variable will be derived from information collected in eCRF section '*Prior intravitreal injections/Corticosteroids in Study eye*' (PII/F6 form).

The variable will be first derived as continuous variable to:

- 0,
- if the variable '*1.0.1 - Prior to first Ozurdex injection in the study eye for DME, did the patient receive any anti-VEGF or Corticosteroid therapy to treat the study eye?*' is equal to 'No',
- or if the variable '*1.0.1 - Prior to first Ozurdex injection in the study eye for DME, did the patient receive any anti-VEGF or Corticosteroid therapy to treat the study eye?*' is ticked to 'Yes', no anti-VEGF treatments are reported and at least one corticosteroid treatment is reported.
- the sum of the numbers of treatments reported for anti-VEGF treatments, if at least one anti-VEGF treatment is reported.

- missing,
  - if the variable '*1.0.1 - Prior to first Ozurdex injection in the study eye for DME, did the patient receive any anti-VEGF or Corticosteroid therapy to treat the study eye?*' is missing
  - or if the variable '*1.0.1 - Prior to first Ozurdex injection in the study eye for DME, did the patient receive any anti-VEGF or Corticosteroid therapy to treat the study eye?*' is equal to 'Yes' and no treatments have been reported in the table (neither anti-VEGF nor corticosteroids treatments)
  - or if the variable '*1.0.1 - Prior to first Ozurdex injection in the study eye for DME, did the patient receive any anti-VEGF or Corticosteroid therapy to treat the study eye?*' is equal to 'Yes' and at least one anti-VEGF treatment is reported with the corresponding number of treatments that is missing.

The continuous variable will be then categorized in the following categories: 0, 1 to 3, 4 to 6, and >6.

Number of corticosteroid treatments in the study eye prior to the first Ozurdex implant injection in the study eye

This variable will be derived in the same way that the variable 'Number of anti-VEGF treatments in the study eye prior to the first Ozurdex implant injection in the study eye' (See definition above) using information from appropriate sections of the eCRF.

At least one anti-VEGF treatment in the study eye before the first Ozurdex injection in the study eye (Yes, No)

The variable will be derived using information reported in eCRF section '*Prior intravitreal injections/Corticosteroids in Study eye*' (PII/F6 form). The variable will be derived to:

- Yes, if at least one anti-VEGF treatment is reported (= check box ticked)
- No,
  - if the variable '*1.0.1 - Prior to first Ozurdex injection in the study eye for DME, did the patient receive any anti-VEGF or Corticosteroid therapy to treat the study eye?*' is equal to 'No',

- or if the variable '*1.0.1 - Prior to first Ozurdex injection in the study eye for DME, did the patient receive any anti-VEGF or Corticosteroid therapy to treat the study eye?*' is ticked to 'Yes', no anti-VEGF treatments are reported and at least one corticosteroid treatment is reported.
- Missing,
  - if the variable '*1.0.1 - Prior to first Ozurdex injection in the study eye for DME, did the patient receive any anti-VEGF or Corticosteroid therapy to treat the study eye?*' is missing
  - or if the variable '*1.0.1 - Prior to first Ozurdex injection in the study eye for DME, did the patient receive any anti-VEGF or Corticosteroid therapy to treat the study eye?*' is equal to 'Yes' and no treatments have been reported in the table (neither anti-VEGF nor corticosteroids treatments)

At least one corticosteroid therapy in the study eye prior to the first Ozurdex implant injection in the study eye (Yes, No).

This variable will be derived in the same way that the variable '*At least one anti-VEGF treatment prior to the first Ozurdex implant injection in the study eye*' (See definition above).

At least one concomitant anti-VEGF treatment in the study eye (Yes, No)

The variable will be derived using the date of the first Ozurdex injection in the study eye (eCRF section '*Inclusion and Exclusion Criteria*' (IE/F1 form)), the side of the study eye (OS/OD, eCRF section '*Demographics and DME history*' (DM/F2 form)) as well as information reported in eCRF section '*Concomitant Medications (inclusive of intravitreal injections, systemic Steroids, and IOP medications)*' (CM/F18 form). The variable will be derived to:

- Yes, if at least one anti-VEGF treatment is reported with '*1.6.1 - Specify eye*' = {the side of the study eye, 'OU'}
- No,
  - If the variable '*1.1 - Were any ophthalmic concomitant medications taken (including intravitreal injections, systemic steroids, and IOP medications)?*' is equal to 'No'

- Or, if the variable '*I.1 - Were any ophthalmic concomitant medications taken (including intravitreal injections, systemic steroids, and IOP medications)?*' is equal to 'Yes' and no anti-VEGF treatments are reported
- Or, anti-VEGF treatment(s) are reported however for all anti-VEGF treatments '*I.6.1 - Specify eye*' is equal to the side of the contralateral eye
- Missing,
  - If the variable '*I.1 - Were any Ophthalmic Concomitant Medications taken (including Intravitreal injections, systemic Steroids, and IOP medications)?*' is missing
  - Or, if the variable '*I.1 - Were any Ophthalmic Concomitant Medications taken (including Intravitreal injections, systemic Steroids, and IOP medications)?*' is equal to 'Yes' however no medications have been reported in the form
  - Or, if at least one anti-VEGF treatment is reported with '*I.6.1 - Specify eye*' that is missing and there is no anti-VEGF treatment reported with '*I.6.1 - Specify eye*' = {the side of the study eye, 'OU'}.

At least one concomitant corticosteroid therapy in the study eye (Yes, No)

This variable will be derived in the same way that the variable '*At least one concomitant anti-VEGF treatment in the study eye*' (See definition above).

At least one concomitant anti-VEGF or corticosteroid therapy in the study eye (Yes, No)

The variable will be defined from the 2 derived variables '*At least one concomitant anti-VEGF treatment in the study eye*' and '*At least one concomitant corticosteroid therapy in the study eye*'. It will be derived to:

- Yes, if '*At least one concomitant anti-VEGF treatment in the study eye*' and/or '*At least one concomitant corticosteroid therapy in the study eye*' is equal to 'Yes'.
- No, if '*At least one concomitant anti-VEGF treatment in the study eye*' and '*At least one concomitant corticosteroid therapy in the study eye*' are both equal to 'No'.
- Missing, if '*At least one concomitant anti-VEGF treatment in the study eye*' and/or '*At least one concomitant corticosteroid therapy in the study eye*' is missing and none of them are equal to 'Yes'.

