### **6.3 SUBGROUPS**

The following subgroups will be considered for analysis:

- Treated with Ozurdex in Switzerland vs. Germany
- Patients who are naïve of any anti-VEGF treatment in the study eye prior to the first Ozurdex injection in the study eye: Yes vs. No [DV].
- Number of anti-VEGF treatments in the study eye prior to the first Ozurdex injection in the study eye: 0, 1 to 3, 4 to 6,  $>6$  [DV].
- Lens status of the study eye during the study period: Phakic throughout vs. Pseudophakic throughout vs. Change from Phakic to Pseudophakic [DV].

- At least one concomitant treatment with anti-VEGF and/or corticosteroids in the study eye: Yes vs. No [DV]

Table 6-1 presents subgroups that will apply for each analysis.

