**Table 6-1 Planned Subgroup Analyses**

Analysis	Subgroups				
Demographics and other baseline characteristics (Section 10.0)	X	Treated with Ozurdex in Switzerland vs. Germany	Patient naïve to anti-VEGF in the study eye prior to the 1 st Ozurdex injection in the study eye: Yes vs. No	Number of anti-VEGF treatments in the study eye prior to baseline: 0, 1 to 3, 4-6, >6	Lens status of the study eye during the study period: Phakic throughout vs. Pseudophakic throughout vs. Change from Phakic to Pseudophakic
Diabetes and DME status (Section 11.0)	X				X
Clinical examination in the study eye (Section 12.0)	X				
Prior and concomitant treatments and surgeries (Section 13.0)	X				
Primary objective (Section 15.1)	X	X	X	X	X
First secondary objective (Section 15.2.1)	X	X	X	X	X
Second secondary objective (Section 15.2.2)	X	X	X		X
Third secondary objective (Section 15.2.3)					
Fourth secondary objective (Section 15.2.4)	X				

The planned subgroup analysis specified in Table 6-1 above may not be performed if the number of patients in the subgroup is too small.

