### 15.2.3 Third Secondary Objective

The secondary objective '*To assess drug effectiveness in patients who are naïve of any anti-VEGF treatment*' will be assessed by carrying out analyses detailed in the paragraph '*Description of drug effectiveness*' in Section 15.2.1 in the subgroup of patients who are naïve of any anti-VEGF treatment in the study eye prior to the first Ozurdex injection in the study eye vs. patients who received at least one anti-VEGF treatment in the study eye prior to the first Ozurdex injection in the study eye. Comparison between both subgroups will be purely descriptive (no statistical tests will be computed).

In addition, a subgroup of patients will be identified by the number of anti-VEGF treatments in the study eye prior to the first Ozurdex injection in the study eye. The number of treatments will be categorized: 0, 1 to 3, 4 to 6,  $>6$  [DV].

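### The prior anti-VEGF category is left missing when one agent's number is missing, even where the recorded numbers prove more than 6, and an overlapping sum rule has no stated precedence

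*SAP*

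**What the plan says.** SAP 6.3 defines a four-level subgroup by "Number of anti-VEGF treatments in the study eye prior to the first Ozurdex injection in the study eye". In Table 6-1 the rows for the primary and first secondary objectives are marked in all five subgroup columns, one of which is "Number of anti-VEGF treatments in the study eye prior to baseline: 0, 1 to 3, 4-6, >6". Section 15.2.3 uses the same grouping for the third secondary objective: "a subgroup of patients will be identified by the number of anti-VEGF treatments in the study eye".

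The count is a total over several agents. SAP 21.3.1 lists "pre-listed treatments: Avastin®, Lucentis®, Eylea® and Macugen" and adds a category for other anti-VEGF therapy. Two of its rules apply to an eye with a ticked anti-VEGF agent:

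- **Sum rule.** The count is "the sum of the numbers of treatments reported for anti-VEGF treatments, if at least one anti-VEGF treatment is reported".
- **Missing rule.** The count is missing if the prior-treatment question is answered Yes and "at least one anti-VEGF treatment is reported with the corresponding number of treatments that is missing".

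The category has no derivation of its own: "The continuous variable will be then categorized in the following categories: 0, 1 to 3, 4 to 6, and >6". Section 21.4 imputes partial dates only, and section 21.1 by default leaves missing values out of percentage denominators.

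**The concern.** The top category has no upper limit, so a lower bound on the count can be enough to place a patient in it. The missing rule discards that information. It makes no exception for recorded numbers that already exceed 6.

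The two rules also overlap. A record with one known and one unknown number satisfies both, and no order is given. Two programmers could code the same patient differently, and the sum rule read literally puts some patients in a category that is certainly or possibly too low.

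What is at stake is the size and completeness of the >6 group in descriptive subgroup tables. A note under Table 6-1 allows a subgroup analysis to be dropped if too few patients remain, so avoidable losses have some cost. SAP 7.0 expects incomplete charts and rules out queries to sites, so a missing number cannot be recovered later.

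**Working it through.** The plan states no figure on this point, so there is none to reproduce. The check has three steps.

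**1. What each rule does to a record.** Braces list the numbers entered for the ticked agents. The lower bound is the recorded sum plus 1 for each ticked agent without a number, because a ticked agent implies at least one treatment.

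| Record | Missing rule | Sum rule, read literally | Lower bound | Category that is certain |
|---|---|---|---|---|
| {7, missing} | missing | 7, so >6 | 7 + 1 = 8 | >6 |
| {12, missing} | missing | 12, so >6 | 12 + 1 = 13 | >6 |
| {8, 4, missing} | missing | 12, so >6 | 12 + 1 = 13 | >6 |
| {6, missing} | missing | 6, so 4 to 6 | 6 + 1 = 7 | >6 |
| {3, 3, missing} | missing | 6, so 4 to 6 | 6 + 1 = 7 | >6 |
| {5, missing} | missing | 5, so 4 to 6 | 5 + 1 = 6 | none |
| {missing} | missing | 0, so 0 | 1 | none |
| {4, 3} | 7, so >6 | 7, so >6 | 7 | >6 |

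The missing rule loses five records whose category is certain. The sum rule saves three of them but misfiles {6, missing} and {3, 3, missing}. It also gives a lone {missing} a count of 0, although the separate Yes/No variable in 21.3.1, which needs only the tick box, would call that eye pretreated.

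**2. Who is exposed.** Let m be the chance that one agent's number is missing, independently between agents. An eye with k agents then has a missing count with probability 1 − (1 − m)^k. The documents give no m, so a range is shown.

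| m | k = 1 | k = 2 | k = 3 |
|---|---|---|---|
| 2% | 2% | 4% | 6% |
| 5% | 5% | 10% | 14% |
| 10% | 10% | 19% | 27% |
| 20% | 20% | 36% | 49% |

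The loss rises with the number of agents. These are shares with any missing number, so they are upper limits on the share that is provably >6. An eye with one agent and no number can never be recovered.

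**3. Illustrative size.** All inputs are assumptions: 60%, 32% and 8% of pretreated eyes had 1, 2 and 3 agents; numbers per agent follow a shifted negative binomial with mean 5 (dispersion 1, 2 and 4 tried); m is 5% to 10%. Simulation gives:

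- 9% to 17% of the >6 eyes have a missing count, against 6% to 12% of the others.
- Per 100 pretreated eyes, about 4 to 8 of the >6 eyes are lost, and 2 to 4 of those are provably >6.
- At dispersion 2 the true >6 share is 47.3%. Under the missing rule it is 46.5% at m = 5% and 45.7% at m = 10%, that is 0.8 and 1.6 points too low. With the lower-bound rule it is 47.6% and 47.9%, that is 0.3 and 0.6 points too high.
- If only 15% of pretreated eyes had several agents, or only 1% of numbers are missing, about 0.1 to 1.5 per 100 are recoverable.

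With 150 patients and up to 50 naïve, about 150 − 50 = 100 are pretreated, so these figures read roughly as patients in this study.

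**The case against.** The strongest reply is that the effect is small and conservative. Setting a total to missing when a component is missing is common practice and is pre-specified. Every rate above is assumed, and even then the >6 share moves by less than 2 percentage points. Prior intravitreal injections belong to the minimum required dataset (Protocol 8.2.4), and entry checks are meant to catch missing key data (Protocol 7.3.2 and 12), so few numbers may be missing. Section 21.1 reports the number of missing observations, so a loss would be visible. All of this stands as to size. The documents do not say that the per-agent number is covered by an entry check, and the SAP's own missing rule anticipates the gap.

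A reader might infer that the primary result is distorted. The documents do not support that. The affected patients stay in the overall primary analysis and in the naïve versus pretreated subgroup. Intervals are summarised within each category, so losing >6 eyes leaves the other categories' results unchanged. Nothing shows that the lost eyes have different intervals from those retained.

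A reader might also infer that heavily pretreated eyes are certain to be the ones lost. Greater loss with more agents follows from the arithmetic if numbers go missing independently. That eyes with several agents are mostly the heavily pretreated ones is plausible, but no figure in the documents shows it.

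Finally, the sum rule would put {8, missing} in >6, so coding it missing is not the only possible reading. The missing rule is the more specific and probably the intended one, but the overlap is itself a reason to edit the section.

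**Conclusion.** The point holds as a minor flaw in a derivation rule. On its natural reading, SAP 21.3.1 leaves eyes uncategorised when >6 is a logical certainty, and nothing elsewhere in the plan repairs this. It also departs from the SAP's own practice: the combined concomitant-treatment variable in the same section is Yes if either component is Yes, even when the other is missing.

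The consequence is confined to the >6 level of a descriptive subgroup in a study that tests no hypothesis. The number of patients lost is unknown. Recoverable patients range from about 0.1 to 4 per 100 pretreated, depending on the assumed number of agents per eye, spread of numbers per agent and rate of missing numbers. The reading of the rule is secure; the size is not.

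**What to change.** In SAP 21.3.1:

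1. State that the missing rule takes precedence over the sum rule for the continuous count, which then stays missing.
2. For the categorical variable only, assign >6 when the recorded numbers plus 1 for each ticked agent without a number is at least 7. Otherwise keep it missing.
3. Report the number of patients with a missing category beside each table that uses the subgroup.

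This takes a few lines of SAP text and about one line of code, with no new data. The rule misclassifies no one, provided that a ticked agent means at least one treatment. Its one drawback is that only >6 can be recovered, because an unknown number has no upper limit that would settle 1 to 3 or 4 to 6. The >6 share may then be very slightly overstated, by under 1 percentage point in the illustration.

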### **21.3.2 Variables Related to IOP-Lowering Medications and Other Ophthalmic Concomitant Medications**

Identification of concomitant IOP-lowering medications

Concomitant IOP-lowering medications will be identified from treatments reported in eCRF section '*Concomitant Medications (inclusive of intravitreal injections, systemic Steroids, and IOP medications)*' (CM/F18 form) as:

- pre-listed treatments: Acetazolamide, Apraclonidine, Bimatoprost, Brimonidine, Brinzolamide, Carbachol, Carteolol, Clonidine, Dorzolamide, Latanoprost, Levobunolol, Pilocarpine.
- treatments reported in the category 'Other': IOP-lowering medications will be identified by an exhaustive review of treatments reported in this category: Tafluprost, Timolol maleate, Travoprost, Bimatoprost, Timolol maleate, Brimonidine; Brinzolamide, Brimonidine; Timolol maleate, Brinzolamide; Timolol maleate, Dorzolamide; Timolol maleate, Latanoprost; Timolol maleate, Travoprost; Timolol maleate

At least one concomitant IOP-lowering medication in the study eye (Yes, No)

This variable will be derived in the same way as the variable '*At least one concomitant anti-VEGF treatment in the study eye (Yes vs. No)*' (See Section 20.3.1).

### Identification of other concomitant ophthalmic medications

Other concomitant ophthalmic medications will be identified from treatments reported in eCRF section '*Concomitant Medications (inclusive of intravitreal injections, systemic Steroids, and IOP medications)*' (CM/F18 form) in the category 'Other'. All ophthalmic treatments other than anti-VEGF, corticosteroids and IOP-lowering medications will be classified as 'Other ophthalmic medications'.

#### At least one other ophthalmic concomitant medication in the study eye (Yes, No)

This variable will be derived in the same way as the variable '*At least one concomitant anti-VEGF treatment in the study eye (Yes vs. No)*' (See Section 21.3.1).

### **21.3.3 Variables Related to Lens Status**

#### At least one change in lens status in the study eye during the follow-up period

Using information from eCRF section '*Biomicroscopy – Lens – Study eye*' (BIL/F8 form), the variable will be derived to:

- Yes, if the variable '*1.0 - Have there been any changes to lens status in the study eye to report at this visit?*' is equal to 'Yes' in at least one follow-up visit
- No, if the variable '*1.0 - Have there been any changes to lens status in the study eye to report at this visit?*' is equal to 'No' at all follow-up visits available for the patient
- Missing, if the variable '*1.0 - Have there been any changes to lens status in the study eye to report at this visit?*' is equal to 'Not in Chart' in at least one follow-up visit and is never equal to 'Yes' at the other follow-up visits.

#### Type of change in lens status in the study eye during the follow-up period

The variable will be defined for all patients with at least one change in lens status from phakic to pseudophakic in the study eye during the follow-up period and will be derived using information collected at baseline and during the follow-up period. For these patients, their baseline measures of lens opacity (nuclear opacity, cortical opacity, and posterior subcapsular opacity) and corresponding grade will be recorded.

